9.3 STATISTICAL ANALYSES

9.3.1 GENERAL APPROACH

Categorical data will be presented as percentages. Continuous data will be presented as medians with interquartile range.

For inferential tests, the p-value of 0.05 will be considered significant; 95% confidence intervals for statistical significance (Type I error) and two-tailed tests will be used.

Nonparametric tests will be used to analyzed any non-normative data.

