A RANDOMIZED CONTROLLED PILOT TRIAL OF A STRUCTURED MOBILE TECHNOLOGY BASED LIFESTYLE PROGRAM VS USUAL CARE FOR PATIENTS WITH NON-ALCOHOLIC FATTY LIVER DISEASE

Protocol Number: HUM 00153750

National Clinical Trial (NCT) Identified Number: TBA

Principal Investigator: [name] MD MSc

Sponsor: University of Michigan

Grant Title: American Association for the Study of Liver Diseases (AASLD) Clinical Translational and Outcomes Research Award (CTORA)

NCT Number: NCT03839082

Grant Number: AWD007197

Funded by: AASLD

Version Number: 3.0

Version Approval Date: 12 November 2019

Summary of Changes from Previous Version:

Affected Section(s)	Summary of Revisions Made	Rationale
Section 1.2	Goal total number of participant was increased from 100 to 120 subjects. Hence, the number of patient in each arm of the study will be 60.	This change is necessary in order to ensure that we have more accurate mean values and provide smaller margin of error.
Section 5.5	Additional recruitment strategies were added. Potential patients will be identified through data direct, EMERSE as well as our general hepatology clinics. Potential participants identified via data direct and our general hepatology clinics will be recruited via phone and text.	Changes will help increase efficiency and speed of recruitment.

Table of Contents

INVES	STIGATOR'S SIGNATURE	
1	PROTOCOL SUMMARY	
1.1	Synopsis	
1.2	Schema	
1.3	Schedule of Activities	3
2	INTRODUCTION	
2.1	Study Rationale	
2.2	Background	
2.3	Risk/Benefit Assessment	
2.	.3.1 Known Potential Risks	
2.	.3.2 Known Potential Benefits	
2.	.3.3 Assessment of Potential Risks and Benefits	6
3	OBJECTIVES AND ENDPOINTS	6
4	STUDY DESIGN	
4.1	Overall Design	
4.2	Scientific Rationale for Study Design	
4.3	Justification for Intervention	
4.4	End-of-Study Definition	
5	STUDY POPULATION	
5.1	Inclusion Criteria	
5.2	Exclusion Criteria	
5.3	Lifestyle Considerations	
5.4	Screen Failures	
5.5	Strategies for Recruitment and Retention	
6	STUDY INTERVENTION(S) OR EXPERIMENTAL MANIPULATION(S)	
6.1	Study Intervention(s)	
	.1.1 Study Intervention or Experimental Manipulation Description	
6.2	Fidelity	
6.	.2.1 Interventionist Training and Tracking	
6.3	Measures to Minimize Bias: Randomization and Blinding	
6.4	Study Intervention/Experimental Manipulation Adherence	
6.5	Concomitant Therapy	
7 PART	STUDY INTERVENTION/EXPERIMENTAL MANIPULATION DISCONTINUATION AND ICIPANT DISCONTINUATION/WITHDRAWAL	

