9.2 SAMPLE SIZE DETERMINATION

Sample size calculations will be made based on the total N for the cohort. Enrollment of 120 patients in the intervention should provide adequate power to assess for parameters associated with \geq 5% reduction in steatosis and weight loss using 80% power, alpha 0.05. We anticipate a dropout rate of up to 20%.

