9.3.2 ANALYSIS OF THE PRIMARY ENDPOINT(S)

The primary outcome is change in steatosis. This will be assessed by VCTE controlled attenuation parameter (CAP). A \geq 5% *reduction* in CAP score at 6-months and maintenance at 12 months as this has been associated with clinically meaningful improvements in outcomes.

For individuals with missing data (participants who do not complete follow-up imaging), we will analyze as modified intention to treat and a separate analysis among those who completed all data collection elements.

Subjects will be analyzed according to a modified intention to treat analysis. Individuals who were randomized but never provided FitBit data will not be included in the final analysis

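### Sections 9.3.1 to 9.3.3 name no between-arm model or baseline covariate and let the data choose the type of test; a prespecified baseline-adjusted analysis would gain precision at no cost in data

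*Combined protocol and SAP*

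**What the plan says.** The inferential method is confined to section 9.3.1. It states that "the p-value of 0.05 will be considered significant", that "two-tailed tests will be used", and that 95% confidence intervals will accompany them, without saying of what quantity. On distribution it says "Nonparametric tests will be used to analyzed any non-normative data", and for description "Continuous data will be presented as medians with interquartile range".

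Section 9.3.2 opens with "The primary outcome is change in steatosis", measured by CAP, and then refers to a reduction of at least 5%. Sections 3 and 9.1 also use that threshold, while sections 1.1 and 4.1 speak of change. Section 9.3.3 lists % weight loss at month 6 and a physical activity threshold. None of these sections names a test, a model, an effect measure or a covariate for comparing the arms.

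The schedules in section 1.3 put VCTE (which yields CAP) and weight at Visit 1 and Visit 2 in both arms. Section 8.1 and a footnote to the schedules allow a recent baseline result to be taken from the medical record instead.

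**The concern.** Three things are left open.

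- **The comparison itself.** A reader cannot tell whether the arms will be compared on month-6 values, change scores or responder proportions, or by which test.
- **The trigger for the nonparametric test.** No normality criterion is given, no test is named, and the plan does not say whether raw values, changes or residuals are checked. Section 6.3 makes the trial open label, so the choice could be made with outcomes and arm both in view. What is estimated may also change with the choice.
- **The use of baseline.** Baseline CAP and weight are available but are not planned as covariates. An unadjusted comparison leaves chance imbalance between two arms of 60 in the estimate and may carry a larger standard error than necessary.

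A pilot should hand the next trial an effect estimate with its interval. The reason recorded for enlarging this one was precision of means: "This change is necessary in order to ensure that we have more accurate mean values and provide smaller margin of error". Medians with an unspecified test do not clearly serve that aim.

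**Working it through.** **Inputs from the documents.** Two-sided alpha 0.05 (9.3.1); "using 80% power, alpha 0.05" (9.2); 60 per arm (4.1); dropout up to 20% (9.2), so 120 × 0.8 / 2 = 48 per arm; increase from 100 to 120 (summary of changes, used only as history).

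**Not given.** Effect size, SD, responder rates, and the correlation ρ between baseline and month-6 values. I take ρ from 0.3 to 0.9 as an assumption.

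**The plan's own figure.** Section 9.2 says "Enrollment of 120 patients in the intervention should provide adequate power", but with no effect size or SD the 120 cannot be reproduced. Back-solving a two-group comparison of means, d = (1.960 + 0.842) × √(2/n), gives d = 0.51 at 60 per arm and 0.57 at 48 per arm. There is no stated assumption to check these against.

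**Value of the 20 added patients.** The variance ratio is 100/120 = 0.833, a cut of 16.7%. The standard error falls by 1 − √0.833 = 8.7%.

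**Value of baseline adjustment against a change score.** Assume equal variances σ² at both times and a linear relation, and ignore the small cost of estimating one slope. The change score has variance 2σ²(1 − ρ), and the adjusted model has residual variance σ²(1 − ρ²). The ratio is (1 − ρ²)/(2(1 − ρ)) = (1 + ρ)/2, so the cut is (1 − ρ)/2. If the change-score test has 80% power at 48 per arm, the adjusted analysis has power Φ(2.802/√((1 + ρ)/2) − 1.960).

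| ρ (assumed) | Variance ratio | Variance cut | 120 patients act like | Power |
|---|---|---|---|---|
| 0.3 | 0.65 | 35% | 185 | 93.5% |
| 0.5 | 0.75 | 25% | 160 | 89.9% |
| 0.7 | 0.85 | 15% | 141 | 86.0% |
| 0.9 | 0.95 | 5% | 126 | 82.0% |

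Break-even with the 20 patients is (1 + ρ)/2 = 0.833, so ρ = 0.667. Below that, adjustment gains more; above it, less.

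**Against unadjusted month-6 values.** The variance ratio is 1 − ρ² and the cut is ρ². Break-even is ρ = √0.1667 = 0.408, and here adjustment gains more *above* that value. Because the plan does not name the comparator, the size of the gain cannot be fixed even for a known ρ.

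**Effect of the nonparametric switch alone.** Under normality the rank test has asymptotic efficiency 3/π = 0.955 against the t-test, so 120 patients act like about 115. The lower bound of 0.864 gives about 104, still above 100. With heavy tails the rank test gains: efficiency 1.24 for t with 5 df and 1.90 for t with 3 df.

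I also simulated a switch triggered by a Shapiro–Wilk test on change scores (3,000 runs, 48 per arm, normal baseline, effect set for about 80% by t-test on change). With normal errors and ρ = 0.5 the switching rule had about the same power as the t-test throughout (79.4% v 79.6%). Against baseline adjustment with robust standard errors:

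- t(3) residuals: about equal at ρ = 0.5 (both about 90%); the rule led at 0.7 (92% v 86%).
- t(5) residuals: adjustment led at ρ = 0.5 (89% v 82%); the rule led at 0.9 (85% v 82%).

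**The case against.** The plan is silent on the model; it does not commit to unadjusted tests. A reader might infer such a commitment from section 9.3.1, but no sentence there makes it. That stands, and the point is one of missing specification.

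A reader might also infer that baseline is ignored. It is not: a CAP reduction and % weight loss are both defined relative to baseline, and sections 4.2 and 9.3.7 plan pre-post comparisons. Only its use as a covariate is absent.

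A third tempting reading is that the switch to rank tests wastes more precision than the 20 extra patients bought. The documents do not support it. The switch costs almost nothing when data are normal and can gain power when tails are heavy. The loss from not adjusting depends on a correlation that is nowhere stated, and against a change score it falls below the value of the 20 patients once ρ passes 0.67. For weight, ρ may be high and the gain small. The variance formula is also derived for a simple difference, so for % weight change it is only a guide.

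Finally, if the ≥5% CAP responder form is primary, the outcome is binary. The normality rule does not apply to it, and none of the linear-model figures carries over.

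**Conclusion.** The point holds as a gap in specification with a free improvement available. No between-arm model and no baseline covariate is named, and the type of test is left to the data without a criterion. For continuous CAP, adjusting for baseline would cut variance by 35% to 5% over ρ from 0.3 to 0.9 against an unadjusted change score, given equal variances and a linear relation. It is worth more than the increase from 100 to 120 only if ρ is below about 0.67. Under those assumptions it is not less precise than the change score, but its size in this trial is unknown.

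The case for prespecification does not depend on ρ: it fixes in advance what is estimated in an open-label trial and gives the pilot a stated effect measure with an interval. This should be changed, but it is not an error that invalidates the design.

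**What to change.** Add to sections 9.3.2 and 9.3.3:

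- **Continuous CAP:** a linear model of month-6 CAP on randomised arm with baseline CAP as covariate and robust standard errors, reporting the adjusted mean difference with 95% CI whatever the distribution.
- **Weight:** % weight change at month 6 on arm, with baseline weight as covariate, reported in the same way.
- **If the ≥5% CAP responder form is primary:** a binary model on arm adjusted for baseline CAP, with the effect measure named.

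In section 9.3.1, keep medians and interquartile ranges for description. Replace the distribution-dependent switch with a named rank test as a sensitivity analysis; it is worth keeping because it may have more power with heavy tails. Cirrhosis is an optional covariate: the documents state stratification by it only for MRE assignment, not for arm allocation.

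The cost is a few sentences of plan text, with no new data and no new patients. It is best done before month-6 outcomes are examined by arm.

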9.3.2 ANALYSIS OF THE PRIMARY ENDPOINT(S)

The primary outcome is change in steatosis. This will be assessed by VCTE controlled attenuation parameter (CAP). A \geq 5% *reduction* in CAP score at 6-months and maintenance at 12 months as this has been associated with clinically meaningful improvements in outcomes.

For individuals with missing data (participants who do not complete follow-up imaging), we will analyze as modified intention to treat and a separate analysis among those who completed all data collection elements.

Subjects will be analyzed according to a modified intention to treat analysis. Individuals who were randomized but never provided FitBit data will not be included in the final analysis

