1.2 SCHEMA

[figure not shown]

Figure 1. All participants will be enrolled in the study for ~12 months and will complete 3 study visits. Individuals randomized to the Intervention arm will have 6 months of intervention followed by 6 months of follow-up to assess for behavior change maintenance. Individuals randomized to the Usual Care Waitlist will be followed for 6 months, after which they will start a 6-month intervention period.

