12 NOVEMBER 2019

		p		nent	
OnCore Calendar Segment	Pre-Study	Consented OnStudy		OnTreatment	Off Study
Study Timeline	Pre-screening (Pre-consent)	Visit 1 Day 1	Visit 2 Day 168 ±7	Phone Call- Intervention Arm Day 252 ±14	Visit 3 Day 336 ±21
EMR Review Eligibility	х				
Informed Consent		х			
Demographics		х			
Clinical history		х			
Randomization		х			
Provide FitBit and Instruction to Intervention Arm		х	х		
Outcome Evaluation					
Vitals + Anthropometrics: blood pressure, height, weight, waist and hip circumference		х	х		х
Blood Work: ¹ hepatic panel, platelets, A1c, fasting insulin, glucose, lipid panel		х	х		х
6MWT		Х	х		х
Hand Grip Strength		х	х		х
Quality of Life Questionnaire ⁴		х	х		х
Physical Activity Survey (IPAQ) ⁴		х	х		х
Motivation to Change Questionnaire ⁴		х	Х		х
Dietary Survey ⁴		х	Х	х	х
Dietician Assessment ²		х			
VCTE ¹		х	Х		х
MRE1 ^{1,3}		х	Х		
Exit Interviews			Х		х
Adverse Events Reporting		х	Х	Х	х

Table 2. Arm II - wait list control; receives intervention after visit 2

¹Baseline results can be abstracted from medical record if performed within prior 6 months and <5% weight change since that time. Otherwise, VCTE will be performed +/- 14 days from enrollment. Hepatic panel and platelet count are standard of care measures. Remainder of imaging and laboratory data will be research costs. ²Can be done +/- 14 days from enrollment in person or via telephone

³ Only done in half of patients due to cost, determined by computer randomization with stratification according to liver disease stage (cirrhosis)

⁴ If not enough time during enrollment, participants will be sent a link via email to complete the surveys within 14 days from enrollment date.

EMR, electronic medical record; 6MWT, 6 minute walk test; IPAQ, International Physical activity Questionnaire; VCTE, vibration controlled transient elastography; MRE, magnetic resonance elastography

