3 OBJECTIVES AND ENDPOINTS

OBJECTIVES	ENDPOINTS	JUSTIFICATION FOR ENDPOINTS
Primary		
Compare the effectiveness of usual care to a mobile technology based lifestyle intervention on change in liver and metabolic related parameters.	Reduction in amount of hepatic steatosis (≥5% overall reduction in CAP score) at 6 months.	Hepatic steatosis is a liver specific outcome that has been shown to improve with diet and exercise and is associated with risk of downstream clinical outcome such as development of NASH and cirrhosis.
Secondary		

OBJECTIVES	ENDPOINTS	JUSTIFICATION FOR ENDPOINTS
Improvements in other liver-specific and metabolic outcomes	weight loss, increase in total physical activity (based on step counts)	Weight loss has been associated with histologic improvements in NAFLD and NASH. Physical activity has been shown to improve fibrosis, liver enzymes, metabolic parameters and HRQOL.

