4 STUDY DESIGN

4.1 OVERALL DESIGN

This randomized clinical pilot trial will compare a mobile technology-based lifestyle intervention to a waitlist control group receiving usual care for adult patients with NAFLD. The intervention will use FitBit to track and promote physical activity through tailored longitudinal feedback. Patient will also receive nutritional counseling with serial nutritional assessments. The primary endpoint will be change in amount of hepatic steatosis. Secondary outcomes include changes in weight and physical activity (assessed by trend in step counts). A wait-list control design will be applied. 60 Patients will be randomized to the intervention arm for 6 months and 60 to usual care (the wait-list control). Those initially randomized to the intervention arm will then transition to a 6-month post intervention monitoring period to assess maintenance of behavior change and sustainability of impact on outcomes of interest. Individuals initially randomized to usual care, will transition to the intervention at month 6 for a total of 6 months.

The intervention arm will receive tailored physical activity and nutritional counseling, and the waitlist control arm which will follow usual and customary care for NAFLD patients attending our Heptology clinic for 6 months and then receive the 6-month intervention.

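### Section 9.3.2 adds an undefined 12-month maintenance element to a primary endpoint that Section 3 sets at 6 months, and at month 12 there is no usual-care control

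*Combined protocol and SAP*

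**What the plan says.** Section 3 gives the primary endpoint as "Reduction in amount of hepatic steatosis (≥5% overall reduction in CAP score) at 6 months", with no later time point. Section 4.1 states only that "The primary endpoint will be change in amount of hepatic steatosis", and the synopsis likewise gives no time point. Section 9.3.2, headed as the analysis of the primary endpoint, refers to a ≥5% reduction "in CAP score at 6-months and maintenance at 12 months". That sentence has no main verb, and nothing after it defines maintenance or gives it a role.

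Three places describe the crossover:
- Section 4.1: "Individuals initially randomized to usual care, will transition to the intervention at month 6 for a total of 6 months".
- The schema in Section 1.2: "Individuals randomized to the Usual Care Waitlist will be followed for 6 months, after which they will start a 6-month intervention period".
- Table 2 of the schedule of activities (Section 1.3): "wait list control; receives intervention after visit 2".

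The arm treated first moves at month 6 to a "6-month post intervention monitoring period to assess maintenance of behavior change and sustainability of impact on outcomes of interest" (Section 4.1). VCTE, which supplies CAP, is scheduled in both arms at Visit 1, Visit 2 (Day 168) and Visit 3 (Day 336).

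**The concern.** Two sections that should fix the same primary endpoint give different time frames, and the later one can be read in at least three ways: a responder must meet the threshold at 6 months and still meet it at 12; months 6 and 12 are both primary time points; or month 12 is descriptive. These give different primary results, and the choice could be made after the data are seen.

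The first two readings also bring in a time point at which the comparison of interest no longer exists. The primary objective in Section 3 compares the intervention with usual care. By Visit 3 the wait-list arm has just finished its 6 months of intervention, and the other arm has been off it for 6 months.

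**Working it through.** **Sections side by side**

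| Place | Time frame or role |
|---|---|
| Section 3, primary endpoint | 6 months only |
| Sections 1.1 and 4.1, primary endpoint | none given |
| Section 9.1, primary hypothesis | completers defined by the 6-month return visit |
| Section 9.3.2, primary analysis | 6 months, plus maintenance at 12 months |
| Section 9.3.3, secondary endpoints | month 6 |
| Section 4.2, post-intervention follow-up | maintenance in those first randomised to the intervention |

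Only Section 9.3.2 attaches month 12 to an efficacy endpoint. No section says how month-12 data from the wait-list arm enter the primary analysis.

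**What each arm has received**

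| | Months 0–6 | Months 6–12 | Between-arm contrast at the end |
|---|---|---|---|
| Immediate arm | intervention | none, monitored | month 6: intervention vs usual care |
| Wait-list arm | usual care | intervention | month 12: immediate-then-off vs delayed |

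**The plan's own figure.** Section 9.2 gives N = 120 with 80% power and alpha 0.05. It cannot be reproduced: no responder rate, SD or effect size is stated, and the power is framed around parameters associated with response. The calculation below is therefore for scale only.

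**Inputs from the plan.** 60 per arm (Section 4.1); dropout up to 20% (Section 9.2), so 60 × 0.80 = 48 per arm if equal in both; two-sided 0.05 (Section 9.3.1).

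**Assumed inputs.** 6-month response 45% (immediate) and 20% (wait-list). Of the 6-month responders, 50–70% in the immediate arm keep the response off intervention, and 70–90% in the wait-list arm keep it while treated.

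**Formula.** With d = |p1 − p2| and p̄ = (p1 + p2)/2:

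power = Φ[(d − 1.96·√(2p̄(1−p̄)/n)) / √((p1(1−p1) + p2(1−p2))/n)]

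At 6 months: d = 0.25, p̄ = 0.325, null SE = √(2 × 0.2194/48) = 0.0956, alternative SE = √((0.2475 + 0.1600)/48) = 0.0921. Power = Φ[(0.25 − 0.1874)/0.0921] = Φ(0.68) = 0.75.

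If success meant response at 6 months and maintained at 12, each rate is the 6-month rate times the retention:

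| Retention, immediate / wait-list | Rates | Difference | Power |
|---|---|---|---|
| 6 months only | 45% vs 20% | 25 points | 0.75 |
| 50% / 90% | 22.5% vs 18% | 4.5 | 0.08 |
| 50% / 70% | 22.5% vs 14% | 8.5 | 0.19 |
| 70% / 90% | 31.5% vs 18% | 13.5 | 0.33 |
| 70% / 70% | 31.5% vs 14% | 17.5 | 0.53 |

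**How much of this is crossover?** Suppose controls stayed untreated and kept their response at the same rate as the immediate arm. At 50% retention the rates are 22.5% vs 10% and power is 0.38. At 70% they are 31.5% vs 14% and power is 0.53. So power would fall from 0.75 to 0.38–0.53 without any crossover. At 50% retention, crossover takes it further, from 0.38 to 0.08–0.19.

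**Sensitivity.** With 50% vs 20% at 6 months, power is 0.88. With 90% wait-list retention and 50%, 70% or 90% retention in the immediate arm, the rates are 25%, 35% or 45% vs 18%, and power is 0.13, 0.47 or 0.82. Dilution occurs when the immediate arm loses more responders, in percentage points, than the wait-list arm. It does so in every case above, but at high retention the loss is small.

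**The case against.** The best reply is that Section 9.3.2 does not do what a reader might infer. It is a sentence fragment: it states no combined 6-and-12-month responder and specifies no between-arm test at month 12. Sections 4.1 and 4.2 describe the post-intervention period as a look at maintenance in those treated first, which is a within-arm purpose. Section 4.2 also speaks of a pre-post analysis, and Section 9.3.7 lists data for one. On that reading the sponsor meant something close to the fix below. This stands as far as it goes: the documents do not support saying that the planned primary analysis mixes two contrasts. But the element sits under the primary-endpoint heading without a secondary or descriptive label, and no other section reconciles it with Section 3.

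Three further inferences are tempting and should be resisted.
- *No randomised control at month 12.* The groups are still the randomised arms. What is missing is a usual-care control.
- *Crossover would reverse the result.* A combined responder must have responded at month 6, so a wait-list participant who first responds after crossover cannot count. The difference stays positive at 4.5–17.5 points. With 90% wait-list retention, reversal needs immediate-arm retention below 18/45 = 40%, outside the assumed range. A negative difference arises more readily for month-12 status alone: 25%, 35% or 45% against an assumed 50% in the newly treated arm gives −25, −15 or −5 points. That is a different endpoint.
- *The fall in power measures the harm of crossover.* Much of it comes from assumed loss of response off intervention.

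It is also fair that this is a pilot and that Section 3 is clear. That limits the consequences but does not settle which section governs.

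**Conclusion.** The point holds as an unreconciled inconsistency with a design consequence. Sections 3 and 9.3.2 differ on the time frame of the primary endpoint, and maintenance is undefined in meaning and role. Any month-12 component cannot estimate intervention versus usual care, because the wait-list arm has by then been treated. This rests on the text alone and on no assumed rate.

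The size is illustrative. Under the assumed 45% vs 20% and 48 per arm, requiring maintenance takes the difference from 25 points to 4.5–17.5 and power from 0.75 to 0.08–0.53. With 50% vs 20%, power goes from 0.88 to between 0.13 and 0.82. The documents supply none of these rates, and only part of the fall is due to crossover.

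**What to change.** In Section 9.3.2, state one primary endpoint that matches Section 3: a ≥5% reduction in CAP from baseline at 6 months, compared between the randomised arms. Keep it as the responder endpoint, since a mean change in CAP would be a different one.

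Make 12-month maintenance a secondary, descriptive estimate within the immediate-intervention arm, and define it. One option is the proportion of that arm still at ≥5% CAP reduction from baseline at month 12, with a 95% confidence interval and a stated denominator. Say how wait-list month-12 data will be used, and present no between-arm test at month 12 as intervention versus usual care.

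The cost is wording, and the small downside is that maintenance loses primary status. Visits, imaging and sample size do not change. With the 6-month endpoint, and usual-care response assumed at 10–40%, the difference detectable with 80% power is about 20–25 points at 60 per arm and 23–28 points at 48 per arm. The change should be made before outcome data are examined.

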4.2 SCIENTIFIC RATIONALE FOR STUDY DESIGN

This trial will incorporate a wait-list control that will allow us to maximize our ability to assess the primary outcome (by using a pre-post intervention analysis). The 6-month post-intervention follow-up among those initially randomized to the intervention will allow us to assess maintenance of behavior change.

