6 STUDY INTERVENTION(S) OR EXPERIMENTAL MANIPULATION(S)

6.1 STUDY INTERVENTION(S)

6.1.1 STUDY INTERVENTION OR EXPERIMENTAL MANIPULATION DESCRIPTION

This is a randomized trial comparing a structured mobile technology-based lifestyle intervention compared to usual care.

Intervention

-Education: Patients in the intervention arm will receive our NAFLD educational folder with an overview of contents by study staff. The folder includes: 1) NAFLD disease information including diagnosis, clinical manifestations, natural history and treatments; 2) NAFLD nutritional recommendations including sample menus; 3) NAFLD physical activity recommendations including walking programs and physical activity logs; 4) weight tracking logs; and 5) resources for diet and exercise programs.

-**Physical Activity**: All participants in the intervention arm (N=60) will receive a FitBit Zip for monitoring of step counts. The Fitbit wirelessly syncs data from the tracker to the Fitbit software or app. Study staff will assist with downloading the software and will instruct participants to wear their FitBit during waking hours every day. At any time if the participant has questions or problems regarding the use of the FitBit, a study staff member can be contacted. Study staff will retrieve users' step count data for analysis weekly and will provide subject with personalized feedback on physical activity with tailored step count goals (10% increase per week with max increase 800 steps per week to a maximum of 10,000 steps/week) and motivational messaging via e-mail. Patients with consecutive days without data recorded or with other signs of low FitBit usage (days with minimal step counts) will be contacted by study staff via e-mail or phone if necessary to encourage use. Feedback will occur weekly for the first 3 months of the intervention and then transition to biweekly for the last 3 months. Participants will also complete the short-version IPAQ for physical activity at enrollment, 6 month and 12 month follow-up visits.

-Nutrition: Patients in the intervention arm will have a nutritional assessment by a GI nutritionist specializing in NAFLD either at the enrollment visit if time allows, or in a separate in person or phone assessment within the first 2 weeks of enrollment. All patients will also complete the "Starting the Conversation" nutritional questionnaire for patients with metabolic disease at enrollment, 6 month and 12 month follow-up visits.(15)

Usual Care

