6.3 MEASURES TO MINIMIZE BIAS: RANDOMIZATION AND BLINDING

Participants in this trial will be randomized to either the intervention arm (tailored physical activity and nutritional counseling) or a wait-list control arm that receives usual care for 6 months, after which they will receive the intervention (for 6 months). Neither participants nor interventionists are blinded to study arm.

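### The final analysis drops anyone who never supplied FitBit data, without naming an arm or period, so the comparison with usual care rests on device use after unblinded randomisation

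*Combined protocol and SAP*

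**What the plan says.** Section 9.3.2 sets the primary analysis on a modified intention-to-treat basis and closes with the rule "Individuals who were randomized but never provided FitBit data will not be included in the final analysis". It adds a completer analysis, but no analysis of everyone randomised and no method for missing CAP. The primary objective (sections 1.1 and 3) is a comparison with usual care, and section 3 places the CAP endpoint at 6 months.

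On who has a device, section 6.1.1 says "All participants in the intervention arm (N=60) will receive a FitBit Zip for monitoring of step counts". On usual care, the note to the schema in section 1.2 says "Individuals randomized to the Usual Care Waitlist will be followed for 6 months, after which they will start a 6-month intervention period". Sections 4.1 and 6.3 agree, as does the Table 2 title in section 1.3: "Table 2. Arm II - wait list control; receives intervention after visit 2". However, Table 2 also marks the row "Provide FitBit and Instruction to Intervention Arm" at Visit 1 as well as Visit 2. Section 3 lists among the secondary endpoints "weight loss, increase in total physical activity (based on step counts"), which as a between-arm outcome would need step data from controls.

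On blinding, section 6.3 says "Neither participants nor interventionists are blinded to study arm".

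**The concern.** Whether a participant ever sends FitBit data is decided after randomisation, with the arm known, and can depend on motivation and on the arm itself. People who never sync may well respond less often. Removing them changes who is compared, and randomisation no longer protects the contrast.

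The rule also has no fixed meaning for controls. Taken literally over 12 months, with the device supplied after month 6, a control's valid 6-month CAP counts only if that person later syncs a device, so inclusion depends on something that happens after the endpoint. Confined to the intervention arm, it removes non-users from one side only. If data were required by month 6 and controls had no device, no control would qualify. If both arms hold a device from Visit 1, it applies to both but still selects after randomisation. The plan does not choose among these, so the choice could be made once outcomes are known.

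**Working it through.** **Inputs.** From the plan: 60 per arm (section 4.1); two-sided tests at 0.05 (section 9.3.1); dropout up to 20%, with no timing given (section 9.2). Responder rates, shares never syncing and timing of dropout are not in the documents and are assumptions. The planned total of 120 cannot be reproduced, because section 9.2 gives no responder rate, standard deviation or effect size; nothing below depends on it.

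All cases assume no true effect, so any expected difference is bias. Type I error comes from 400,000 simulated trials per case, using a pooled two-sided z-test.

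**1. Rule applied to the intervention arm only.** Let f be the share who never sync, pe the responder rate of those who sync and pn that of those who never sync. The kept intervention group responds at pe and the full control arm at (1 - f)pe + f·pn, so bias = f(pe - pn).

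| f | 35% vs 10%: bias | type I error | 40% vs 0%: bias | type I error |
|---|---|---|---|---|
| 5% | 0.05 × 0.25 = +1.25 points | 5.3% | 0.05 × 0.40 = +2.0 points | 5.6% |
| 10% | +2.5 points | 6.1% | +4.0 points | 7.4% |
| 20% | +5.0 points | 8.8% | +8.0 points | 14.1% |

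A separate calculation by normal approximation held the overall rate at 30% in both arms and used (0.30 - f·r)/(1 - f), where r is the never-users' rate. For r = 10% and f = 5%, 10%, 20%, the bias is +1.1, +2.2, +5.0 points and rejection 5.2%, 5.8%, 8.6%. For r = 0 it is +1.6, +3.3, +7.5 points and 5.4%, 6.7%, 13.1%.

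**2. Rule applied to both arms over 12 months, device for controls after month 6, missing CAP counted as failure.** Let d be the share leaving each arm before month 6 and p the responder rate among those who stay. Intervention leavers have synced at least once and stay in as failures. Control leavers never had a device and are removed. Bias = p(1 - d) - p = -p·d.

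- p = 20%, d = 10%: -2 points, type I error 6.1%
- p = 30%, d = 20%: -6 points, 10.9%
- p = 40%, d = 20%: -8 points, 14.1%

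**3. Same reading, observed CAP only.** Suppose 20% of each arm are potential non-users, and shares x = f (intervention) and x = g (control) of the whole arm are actually excluded. The kept rate is k(x) = [0.8·pe + (0.2 - x)·pn]/(1 - x), and bias = k(f) - k(g). With pe = 40% and pn = 0:

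- f = 20%, g = 0: 0.32/0.80 - 0.32 = +8 points
- f = 0, g = 20%: -8 points
- f = 5%, g = 10%: 0.32/0.95 - 0.32/0.90 = -1.9 points
- f = g: 0

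The 30% calculation in step 1 shows the same change of sign. With r = 10% and 10% of the intervention arm excluded, excluding 5%, 10%, 20% or 30% of controls gives +1.2, 0, -2.8 or -6.4 points.

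**4. Data required by month 6, controls without a device.** All 60 controls are excluded and no comparison remains.

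**5. Both arms hold a device from Visit 1.** The step 3 formula applies. Bias is zero only if the share and outcomes of never-syncers match between arms, which an open-label trial cannot guarantee.

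**Reference.** Analysing all randomised participants gives zero expected difference and type I error of 5.0% to 5.3%.

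**The case against.** The strongest objection is that the primary analysis may not be between arms at all. Section 9.3.2 names no between-arm test, section 9.1 frames the primary hypothesis around people who complete the intervention, section 9.2 counts 120 patients as receiving it, and section 4.2 says the design will "maximize our ability to assess the primary outcome (by using a pre-post intervention analysis"). In a pooled before-and-after analysis the rule is more coherent. That is true, but the stated primary objective is comparison with usual care, and no other analysis set is offered for it.

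Second, the literal sense of never is the whole time on study, so the month-6 reading adds a condition that is not in the text. This stands. The empty control arm follows only from that added condition. Likewise, bias can be zero if never-syncers match between arms.

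Third, the Table 2 tick at Visit 1 may be a copied row, since its label names the intervention arm. Section 9.3.3 also bases the month-6 activity endpoint on IPAQ and not on step counts. Both points are fair, and they are why the passages need reconciling. The exclusion is a problem whichever way that is settled.

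Fourth, the larger figures need many never-syncers with very poor response. Eligibility requires a compatible device, and staff help with set-up and contact low users. At 1% to 2% never syncing in the intervention arm only, bias is about 0.3 to 0.8 points and type I error 5.1% to 5.2%. At 5%, the lower figure of 5.3% lies within the range for the all-randomised analysis. The 20% dropout limit is not a never-sync rate, and counting missing CAP as failure is not the plan's rule. This limits the likely size and leaves the defect in place.

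Finally, this is a pilot. It nevertheless plans two-sided tests at 0.05 and hypothesises significantly better outcomes than usual care.

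**Conclusion.** The concern holds and should be corrected before analysis. As written, the primary analysis set depends on device use after unblinded randomisation, and the plan does not say to whom or over what period the rule applies. The comparison with usual care is therefore unprotected by randomisation, and the direction of any bias depends on an unstated choice.

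On assumed rates the bias ranges from about +1 to +8 points in the intervention-only reading at 5% to 20% never syncing, through -2 to -8 points in the 12-month reading with missing counted as failure, to anywhere from -8 to +8 points on observed CAP. The upper figures rest on extreme assumptions; with very few never-syncers the effect is negligible. The actual size cannot be known from the documents.

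**What to change.** - In section 9.3.2, delete the FitBit exclusion from the primary analysis and analyse all randomised participants in their assigned arm.
- State one method for missing 6-month CAP, for example a likelihood-based model or multiple imputation using arm, baseline CAP and weight. Keep the completer analysis as a sensitivity analysis.
- A FitBit-based set may remain as a further sensitivity analysis if its arm and time window are stated. Otherwise report FitBit use as adherence, where section 6.4 already places it.
- Reconcile the Visit 1 FitBit entry in Table 2 with sections 1.2, 4.1, 6.1.1 and 6.3.
- As a side point, section 7.2 allows some randomised participants to be replaced. State that they stay in the analysis even if extra participants are enrolled.

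The cost is a few sentences and some additional analysis for missing CAP, with no new data collection. The estimate may be less favourable because non-users are kept.
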